#### 9.4.3 Analysis of Other Endpoint(s)

Provide the re-operation rate in older patients vs. younger patients for both the displaced and non-displaced fracture types.

### 9.5 SAFETY ANALYSES

All safety analyses will be conducted using the safety population. The number of incidences and number of subjects reporting all adverse events will be summarized both overall and by

#### CONFIDENTIAL AND PROPRIETARY

This document contains information that is confidential and proprietary to Smith & Nephew PLC and Smith & Nephew, Inc. and is intended for use only by Smith & Nephew and its manufacturer. It shall not be reproduced or copied in whole or in part, nor shall the contents be disclosed by any means without prior written permission from Smith & Nephew, nor shall anyone make any use of it that is contrary to the expressed or implied wishes of Smith & Nephew.

Study Protocol—Device	
A Multicenter, Post Market, Prospective Study Evaluating Safety and Efficacy of CONQUEST FN™ for the Treatment of Intracapsular Femoral Neck Fractures	Number: 18-3047-02
	Version: 2.0, 30Nov2018
	Page: Page 35 of 63

seriousness, severity, relationship to study device and outcome. Incidences and number of subjects reporting device deficiencies will also be summarized. Further summaries of safety data may be described in the SAP.

## **9.6 INTERIM ANALYSES**

Once the last subject passes 6 Months, an interim analysis composed of summarizing the outcome and safety data will be performed. Additional unscheduled interim analyses may be performed during the conduct of this study to support requests from regulatory authorities and scientific publications.

## **10. SAMPLE SIZE JUSTIFICATION**

Precision Analysis was used to assess the overall proportion of re-operation rate for any reason of displaced and non-displaced femoral neck fractures treated with the CONQUEST FN™ Femoral Neck Fracture System at one-year post-operation. Assuming a 5% lost to follow-up rate after the first year, a minimum of 90 subjects will be enrolled (based on the inclusion/exclusion criteria) in order to complete 80 evaluable subjects. The 90 subjects will be enrolled to allow a minimum of 45 subjects with each of the following indications to be recruited: displaced or non-displaced femoral neck fractures. For the displaced group this number of subjects is sufficient to estimate the proportion of success rate to within 12% by use of the two-sided 95% confidence interval (assuming an overall success rate of 87%). And for the non-displaced group this number of subjects is sufficient to estimate the proportion of success rate to within 10% use of the two-sided 95% confidence interval (assuming an overall success rate of 93%).

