#### **7.5 ENROLLMENT**

Enrollment in this study shall occur once the subject has successfully completed the informed consent process and successfully completed the Operative Visit (Day 1). A subject number will be assigned at the time of the Screening visit.

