## 9.4 EFFICACY ANALYSIS

The study is non-comparative and non-randomized, single cohort, post-marketing, multicenter prospective study to evaluate the clinical outcomes of the CONQUEST FN™ Femoral Neck Fracture System. A minimum total of 90 subjects will be enrolled in the study, which includes a 5% estimate for subjects lost to follow-up at 1 year.

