#### 9.4.1 Analysis of Primary Endpoint

A two-sided confidence interval will be provided for the proportion of re-operation (i.e. re-operation rate) for any reason of displaced and non-displaced femoral neck fractures treated with CONQUEST FN™ at one-year post-operation.

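### The plan allows for 5% loss between 90 enrolled and 80 evaluable, which is an 11.1% drop, and does not say whether a subject re-operated and withdrawn early is evaluable

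*Combined protocol and SAP*

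**What the plan says.** Section 10 gives one attrition term and two totals: "Assuming a 5% lost to follow-up rate after the first year, a minimum of 90 subjects will be enrolled", and the purpose is "in order to complete 80 evaluable subjects". Section 9.4 describes the minimum of 90 as a number "which includes a 5% estimate for subjects lost to follow-up at 1 year". Neither section gives an allowance for death, withdrawal or exclusion.

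Section 10 then moves to the fracture groups: "The 90 subjects will be enrolled to allow a minimum of 45 subjects with each of the following indications to be recruited". The precision statements come next: "For the displaced group this number of subjects is sufficient to estimate the proportion of success rate to within 12" per cent, at an assumed success rate of 87%, and "for the non-displaced group this number of subjects is sufficient to estimate the proportion of success rate to within 10" per cent, at an assumed 93%. Both refer to two-sided 95% confidence intervals. Section 9.4.1 adds only that "A two-sided confidence interval will be provided for the proportion of re-operation".

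Four other sections bear on who ends up evaluable:

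- Section 7.5 places enrolment after the subject has "successfully completed the Operative Visit (Day 1").
- The replacement policy in Section 7.7.1 does not replace anyone who drops out after enrolment.
- Section 7.7.1 also lists revision or exchange of any original hardware component among the reasons for which the investigator may withdraw a subject.
- Section 9.2 assigns the primary analysis to the Full Analysis Set (FAS) and the Per-Protocol set. The FAS requires at least one assessment after baseline. None of the four sets is called evaluable.

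**The concern.** Precision is the only justification given for the sample size, so a reader should be able to get from 90 to 80 with the stated allowance. That is not possible. It is therefore unclear whether the plan is for 80 or for about 85 evaluable subjects, and which kinds of missing outcome were foreseen.

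The undefined term matters more than the count. The primary endpoint is re-operation for any reason at one year. Surgical revision of the hardware is such a re-operation, and it is also a listed ground for withdrawal. If withdrawal removes the subject from the analysed set, the event is removed too, and the reported rate falls.

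**Working it through.** **Inputs.** 90 enrolled, 80 evaluable and 5% lost to follow-up (Section 10; the 90 and the 5% are repeated in Section 9.4). 45 recruited per group, success rates of 87% and 93%, margins of 12% and 10%, two-sided 95% (Section 10).

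**1. Trying to reproduce 90.**
- Evaluable ÷ (1 − loss): 80 / 0.95 = 84.2, so 85.
- The cruder 80 × 1.05 = 84.
- By group: 40 / 0.95 = 42.1, so 43 each and 86 in total.

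None gives 90.

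**2. The reverse direction.** 90 × 0.95 = 85.5, or 45 × 0.95 = 42.75 per group, rather than 80. The drop from 90 to 80 is 10 / 90 = 11.1%. Five per cent accounts for 90 × 0.05 = 4.5 subjects; the other 5.5 have no stated reason. Screen failures at surgery cannot supply them, because such subjects are never enrolled (Sections 7.5 and 8.4.3).

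**3. What would reconcile the figures.** A 10% all-cause allowance gives 40 / 0.90 = 44.4, so 45 per group and 90 in total. The documents do not say that this is how 90 was reached.

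**4. Do the margins survive at 80?** The documents give no evaluable number per group; 40 assumes an equal split. The Wald half-width is 1.96 × √(p(1 − p)/n):
- Displaced: 1.96 × √(0.87 × 0.13 / 40) = 10.4%.
- Non-displaced: 1.96 × √(0.93 × 0.07 / 40) = 7.9%.

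The Clopper-Pearson half-width is (upper − lower)/2, evaluated at exactly the assumed rate:
- Displaced: (95.5 − 72.6)/2 = 11.5%.
- Non-displaced: (98.6 − 80.3)/2 = 9.2%.

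| n per group | Wald, displaced / non-displaced | Clopper-Pearson, displaced / non-displaced |
|---|---|---|
| 45 | 9.8% / 7.5% | 10.8% / 8.6% |
| 43 | 10.1% / 7.6% | 11.0% / 8.8% |
| 40 | 10.4% / 7.9% | 11.5% / 9.2% |

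All are within 12% and 10%. The assumed rates do not correspond to whole subjects at 40. With whole counts, Clopper-Pearson gives 11.3% for 35 successes and 12.1% for 34 (displaced), and 9.4% for 37 (non-displaced). An observed rate slightly worse than assumed can therefore just exceed 12%.

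**5. What a lost event would do.** If success means no re-operation, the assumed rates imply 45 × 0.13 + 45 × 0.07 = 5.85 + 3.15 = 9.0 re-operations in 90, or 10.0%. As an illustration only, leaving one such subject out of numerator and denominator gives 8 / 89 = 9.0%; leaving out three gives 6 / 87 = 6.9%.

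**6. Whether the plan's sets prevent this.** Surgery and discharge data belong to the visit that Section 8.4.3 calls baseline, so the first scheduled later assessment is at 6 weeks. A subject revised and withdrawn before then may have no post-baseline assessment. That subject would fall outside the FAS, and outside the Per-Protocol set, which is a subset of it.

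**The case against.** The strongest reply is that nothing fails. Section 10 sets a minimum of 90; at 5% loss 85 would do, so 90 is sufficient. Lost to follow-up and not evaluable are different quantities, and Sections 7.7.1, 9.2 and 9.3 name other ways out (withdrawal, protocol deviation, death). This stands as far as size goes. It does not make the figures agree, because no allowance for those other routes is given.

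On re-operated subjects, withdrawal is optional, Section 7.7.3 lets data up to a withdrawal of consent be used, Section 9.3 promises an account of revisions, and the section headed Discontinued Subjects asks for an exit visit where possible. These make the loss of an event less likely. None says that the subject stays in the primary denominator. A reader might infer that the plan drops re-operated subjects; the documents do not say so. They leave the early case open.

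A reader might also infer that the margins, worded on 45 recruited, are missed once attrition is taken off. Step 4 shows otherwise. It is true that the longer, lower arm of a Clopper-Pearson interval is 13.4% and 11.7% at 45 per group, and 14.4% and 12.7% at 40. But Section 10 names no interval and does not say that the margin refers to the longer arm, so this is a reason to define the margin as a half-width and no proof of a shortfall. Section 9 leaves further analysis detail to a later SAP, so not naming the interval method is not an error.

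**Conclusion.** The stated attrition does not connect the stated totals: 5% against 11.1%, or about 85 to 86 evaluable against 80. The error is conservative. The documents do not support a reading that the trial is undersized or that its precision claim fails: the half-widths at 40 per group are 11.5% and 9.2% (Clopper-Pearson) or 10.4% and 7.9% (Wald), against 12% and 10%. That rests on an equal split of the 80, on success meaning no re-operation (Section 10 does not define it), and on the margin being a half-width.

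The undefined evaluable set is the more consequential part. A subject re-operated and withdrawn before 6 weeks could be missing from the primary rate. How many such subjects there might be cannot be derived from the documents. With about 9 events expected, each one left out lowers the rate by about one percentage point. Both parts should be corrected.

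**What to change.** 1. In Sections 10 and 9.4, keep 90 enrolled and make the other two figures agree. Either state an all-cause non-evaluable allowance of about 10% to 11%, with the sponsor's own basis for it, and keep 80; or keep 5% and restate the target as about 85 evaluable (42 to 43 per group).
2. Define evaluable as one-year re-operation status known among enrolled, implanted subjects. This also avoids relying on the FAS as worded, which refers to randomized subjects although Section 8.2 says the study is not randomized. State that any subject re-operated within one year counts as an event and stays in the denominator, even if withdrawn afterwards or without a later visit.
3. When restating Section 10, give the 12% and 10% margins as half-widths on the evaluable number per group, and say that success means no re-operation if that is intended.

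The cost is a wording amendment, which needs signatory and IRB approval under Section 14. Under the first option the stated attrition also looks less favourable. No extra patients are needed.

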## **11. ADVERSE EVENTS AND DEVICE DEFICIENCIES**

### **11.1 DEFINITIONS**

The categories of adverse events are shown in table 12.1-1. The definitions for each of these categories are given in the subsequent sections (see reference within the table).

**Table 12.1-1: Categories of Adverse Event**

	NOT DEVICE-RELATED	DEVICE- OR PROCEDURE-RELATED	
NON-SERIOUS	ADVERSE EVENT (AE) (SEE 12.1.1)	ADVERSE DEVICE EFFECT (ADE) (SEE 12.1.2)	
SERIOUS	SERIOUS ADVERSE EVENT (SAE) (SEE 12.1.3)	SERIOUS ADVERSE DEVICE EFFECT (SADE) (SEE 12.1.3)	
		ANTICIPATED	UNANTICIPATED
		ANTICIPATED SERIOUS ADVERSE DEVICE EFFECT (ASADE) (SEE 12.1.4)	UNANTICIPATED SERIOUS ADVERSE DEVICE EFFECT (USADE) (SEE 12.1.4)

### 11.1.1 Adverse Event

An Adverse Event (AE) is any untoward medical occurrence temporally associated with the use of a study device, whether or not considered causally related to that study device.

AE is used both to refer to AE which are non-serious non-study device or procedure-related and as an umbrella term referring to adverse events of all classifications.

An AE can be any unfavorable and unintended sign (for example, an abnormal laboratory finding), symptom, or disease. For reporting purposes, emphasis is placed first and foremost on whether or not the event constitutes an untoward medical occurrence.

### 11.1.2 Adverse Device Effect

An Adverse Device Effect (ADE) is an adverse event that, in the opinion of the Investigator, is related to the study device or the procedure.

#### CONFIDENTIAL AND PROPRIETARY

This document contains information that is confidential and proprietary to Smith & Nephew PLC and Smith & Nephew, Inc. and is intended for use only by Smith & Nephew and its manufacturer. It shall not be reproduced or copied in whole or in part, nor shall the contents be disclosed by any means without prior written permission from Smith & Nephew, nor shall anyone make any use of it that is contrary to the expressed or implied wishes of Smith & Nephew.

Study Protocol—Device	
A Multicenter, Post Market, Prospective Study Evaluating Safety and Efficacy of CONQUEST FN™ for the Treatment of Intracapsular Femoral Neck Fractures	Number: 18-3047-02 Version: 2.0, 30Nov2018 Page: Page 37 of 63

**Not Related** - An AE is considered to be not related to the use of a study device or the procedure when the effect is DEFINITELY UNRELATED or UNLIKELY to have any relationship to the use of the study device or the procedure;

**Related** – An AE is considered to be related to the use of a study device or the procedure when there is a POSSIBLE, PROBABLE, or DEFINITE relationship between the AE and the use of the study device or the procedure.

An ADE is further categorized depending on whether the criteria in section 12.1.3 and 12.1.4 are met.

### 11.1.3 Serious Adverse Events and Serious Adverse Device Effects

An AE or ADE is considered a **Serious** Adverse Event (SAE) or **Serious** Adverse Device Effects (SADE) if, in the view of either the Investigator or the Sponsor, it:

- a) led to death,
- b) led to serious deterioration in the health of the subject, that either resulted in
  - 1) a life-threatening illness or injury, or
  - 2) a permanent impairment of a body structure or a body function, or
  - 3) in-patient or prolonged hospitalization, or
  - 4) medical or surgical intervention to prevent life-threatening illness or injury or permanent impairment to a body structure or a body function,
- c) led to foetal distress, foetal death or a congenital abnormality or birth defect

*Note 1 to entry: Planned hospitalization for a pre-existing condition, or a procedure required by the CIP, without serious deterioration in health, is not considered a serious adverse event.*

Medical and scientific judgment should be exercised in deciding whether other situations should be considered serious such as important medical events that might not be immediately life-threatening or result in death or hospitalization but might jeopardize the subject or might require intervention to prevent one of the other outcomes listed in the definition above.

#### **11.1.4 Anticipated/Unanticipated Serious Adverse Device Effect**

An Unanticipated Serious Adverse Device Effect (USADE) is a serious ADE which by its nature, incidence, severity or outcome has not been identified in the current version of the risk analysis report.

*Note 1 to entry: Anticipated serious adverse device effect (ASADE) is an effect which by its nature, incidence, severity or outcome has been identified in the risk analysis report. *

#### **11.1.5 Severity**

The severity of every AE will be assessed by the PI or medically qualified site staff to whom the responsibility has been delegated and documented on the delegation of authority log. AE should be classified as mild, moderate, or severe, regardless of whether or not the AE are considered to be serious or non-serious. The classification should be based on the following definitions:

**Mild -** An event is mild if the subject is aware of, but can easily tolerate the sign or symptom;

**Moderate -** An event is moderate if the sign or symptom results in discomfort significant enough to cause interference with the subject's usual activities;

**Severe -** An event is severe if the sign or symptom is incapacitating and results in the subject's inability to work or engage in their usual activities.

#### **11.1.6 Device Deficiency**

A Device Deficiency (DevD) is an inadequacy of a medical device with respect to its identity, quality, durability, reliability, safety or performance. DevD includes malfunctions, use errors and inadequate labelling.

### **11.2 REPORTING PROCEDURES**

AE of any kind and DevD will be recorded in the applicable CRF and source notes. The Investigator will evaluate all AE for relationship to the device and procedure, if applicable,

#### **CONFIDENTIAL AND PROPRIETARY**

This document contains information that is confidential and proprietary to Smith & Nephew PLC and Smith & Nephew, Inc. and is intended for use only by Smith & Nephew and its manufacturer. It shall not be reproduced or copied in whole or in part, nor shall the contents be disclosed by any means without prior written permission from Smith & Nephew, nor shall anyone make any use of it that is contrary to the expressed or implied wishes of Smith & Nephew.

Study Protocol—Device	
A Multicenter, Post Market, Prospective Study Evaluating Safety and Efficacy of CONQUEST FN™ for the Treatment of Intracapsular Femoral Neck Fractures	Number: 18-3047-02
	Version: 2.0, 30Nov2018
	Page: Page 39 of 63

seriousness, and severity. ADE, SAE, and DevD will be entered into the CRF and reported to the Sponsor within 24 hours of the investigator being informed about the event (Figure 12.2-1). For ADE and DevD, details of the product/procedure related to the event will be included and where applicable, pictures taken of the device. The deficient product should be retained for return to S&N unless it is contaminated (e.g. used dressings must not be retained). Updates to submitted information will be recorded in the CRF within 24 hours of the information being available to the investigator.

All adverse events, including SAE and ADE, will be reviewed by a medically qualified person appointed by the Sponsor to determine which, if any, meet criteria for expedited reporting to the regulatory authorities.

The investigator will inform the IRB/IEC of adverse events according to the IRB/IEC requirements.

[figure not shown]
Depending on the nature of the adverse event, S&N may request copies of the subject's medical records, Imaging, Operative notes, as well as results of any relevant laboratory tests performed or other documentation related to the AE. If the subject was hospitalized, a copy of the discharge summary may be requested by S&N and should be forwarded as soon as it becomes available. In certain cases, S&N also may request a letter from the Investigator that summarizes the events related to the case.

**Figure 11.2-1: Evaluation and Reporting of AE and DevD**

### 11.3 FOLLOW-UP OF SUBJECTS WITH ADVERSE EVENTS

For subjects who are experiencing ongoing unresolved AE at the time of their study completion or early discontinuation from the study, it is recommended that the Investigator schedule an appropriate follow-up visit in order to determine the outcome of the event.

#### CONFIDENTIAL AND PROPRIETARY

This document contains information that is confidential and proprietary to Smith & Nephew PLC and Smith & Nephew, Inc. and is intended for use only by Smith & Nephew and its manufacturer. It shall not be reproduced or copied in whole or in part, nor shall the contents be disclosed by any means without prior written permission from Smith & Nephew, nor shall anyone make any use of it that is contrary to the expressed or implied wishes of Smith & Nephew.

Study Protocol—Device	
A Multicenter, Post Market, Prospective Study Evaluating Safety and Efficacy of CONQUEST FN™ for the Treatment of Intracapsular Femoral Neck Fractures	Number: 18-3047-02
	Version: 2.0, 30Nov2018
	Page: Page 41 of 63

Any additional data must be documented and available to the Sponsor who will determine whether the data need to be documented within the CRF.

#### **11.3.1 Ongoing Adverse Events at Study Discontinuation**

Adverse events which are **related** to a study procedure or S&N study device and are ongoing at end of subject's participation: The event should be followed until it is either resolved or until the event has become chronic and is not expected to further improve based on Investigator's review of the event.

Adverse events which are **not related** to a study procedure or S&N study device and are ongoing at end of subject's participation should be followed for 30 days after discontinuation or if the AE is resolved, whichever is sooner.

At the time of data analysis (e.g. interim or final), an evaluation of ongoing events should take place and be listed as ongoing in the safety table.

### **12. INVESTIGATOR OBLIGATIONS**

The Principal Investigator will comply with Good Clinical Practice (GCP), and all applicable regulatory requirements as outlined in Appendix 20.3 of this protocol.

### **13. SPONSOR AND MONITOR RESPONSIBILITIES**

The Sponsor will designate a monitor to conduct the appropriate site visits at the appropriate intervals. The clinical investigation will be monitored to ensure that: the rights and wellbeing of the subjects are protected; the reported data are accurate, complete, and verifiable from the source documents; and the study is conducted in compliance with the currently approved protocol, with GCP regulations, and with applicable regulatory requirements.

Detailed monitoring requirements will be documented within the Clinical Monitoring Plan for this study.

### **13.1 SITE QUALIFICATION VISIT**

A site qualification visit may be performed by the Sponsor prior to the execution of a clinical agreement to ensure that all Investigators have the appropriate training, staff, facilities, and resources to adequately conduct the study.

### **13.2 SITE INITIATION VISIT**

A site initiation visit to provide training on the specifics of the study, site obligations and expectations of study conduct will be performed by the Sponsor or qualified person designated by the Sponsor following the execution of the CTA and documented IRB approval.

